8.5. Safety results

All safety data will be evaluated at the first 34 months period of the study. Additionally, symptomatic skeletal related events will be evaluated at the 2-years safety extension after the end of the treatment.

Analysis of safety-related data will be considered at three levels:

- First, the degree of exposure (dose, duration, number of patients) will be assessed to determine the degree to which study safety can be assessed.
- Second, clinically relevant tests, concomitant medications, and reported AEs will be described. For AEs, severity, expectedness, causality, relationship, body system, action taken, and outcome will be reported.
- Third, SAEs, deaths, and study discontinuations for each study group will be described and assessed.

8.6. Missing data management

The analysis of the primary and secondary timed endpoints (progression and death) will be based on a Log-Rank or Cox regression tests and, therefore, not affected by patient withdrawals (as they will be censored) provided that dropping out is unrelated to prognosis. Patients with missing information in other outcomes, such as clinical benefit rate or overall response, will be considered as no responders. Furthermore, we will report reasons for withdrawal for each randomization group and compare the reasons qualitatively.

8.7. Scientific committee review

A Steering Committee (SC) has been established for this study. Initially, it is composed of the investigators, the study medical scientist, the Scientific Global Coordinator and two physicians expert in radium-223 management.

The SC will meet on demand to review, discuss and evaluate all of the gathered safety data. In case of any arising safety concern, these meetings can also be called at any time at request of a participating investigator. At these meetings, MedSIR and the participating investigators must reach a consensus on safety data. MedSIR will prepare minutes from these meetings and circulate them to each investigator for comment prior to finalization.

The study site Investigators and MedSIR will review patient data at least every four months. Each study site Investigator will monitor patients data for serious toxicities on an ongoing basis.

9. ETHICAL CONSIDERATIONS

9.1. *Regulatory and ethical compliance*

The study will be conducted and reported in accordance with the protocol, the International Conference on Harmonization (ICH) guidelines, the ethical principles laid down in the Declaration of Helsinki, European Clinical Trials Regulation (Regulation (EU) No. 536/2014), and any applicable regulatory requirement.

9.2. *EC*

The conduct of the study must be authorized by a duly constituted EC. Authorization is required for study protocol, protocol amendments, informed consent forms, patient information sheets, and promotional materials.

Wherever necessary, the investigator and/or Sponsor should contact the EC to ensure that accurate and timely information is being provided at every phase of the study.

The principal investigator and/or Sponsor are responsible for providing, when required, written summaries of the study status to the EC annually or more frequently, in accordance with the requirements, policies and procedures set out by the EC. The investigators are also responsible for immediately informing the EC of any protocol amendment.

In addition to reporting the AEs defined in the protocol to the Sponsor, the investigators must immediately report any unexpected issues that entail a risk to patients to their respective ECs. Some ECs may request immediate reporting of all SAEs, while others may only require reporting of events if they are serious, related to the study treatment or unexpected. The Sponsor may provide the investigators with written safety reports or other safety-related reports. Safety reports should be made available to the EC for review and processing in accordance with the regulatory requirements and policies and procedures established by the EC and kept on file at the study site.

9.3. *Informed consent*

Before any protocol-related activity, the signed informed consent should be obtained from each patient. As part of this procedure, the study site investigator or his/her representative should explain verbally and in writing, the nature, duration and purpose of the study, as well as the action of the drugs so that the patient is aware of the possible risks, discomfort and adverse effects that may occur. Study patients will be informed of their right to withdraw from the study at any time and without any reason. The patient will receive all the information required by local regulations and ICH guidelines.

Consent forms must be signed and dated by the patient or their authorized legal representative before starting their participation in the study. Each patient's medical history or medical records should include an entry detailing the process of obtaining informed consent and that it was obtained in writing before the patient's participation in the study.

One copy of the signed consent form should be provided to the patient or the patient's authorized legal representative.

Signed and dated consent forms should be kept in each patient's study file. They should be made available to study monitors who may request them for review at any time.

Consent forms should be reviewed whenever changes have been made to the procedures described in the informed consent or when new information becomes available that may affect the patient's willingness to participate.

In case of review or update of consent forms, each patient's medical history should include an entry detailing the process of obtaining informed consent and that it was obtained in writing using the updated/reviewed consent form in order to continue their participation in the study. The final informed consent form approved by the EC should be provided to the Sponsor for regulatory purposes.

9.4. Data protection

The Sponsor will ensure confidentiality of the patient's medical information, in accordance with the applicable laws and regulations.

The study Sponsor, as data controller according to the European Directive on the protection of individuals with regard to the processing of personal data and on the free movement of such data confirms herewith compliance with Regulation (EU) 2016/679 of the European Parliament and of the Council, of 27 April 2016, on the protection of natural persons with regard to the processing of personal data and on the free movement of such data in all stages of data management.

The data generated by this study will be made available to the representatives of national and local Health Authorities, Sponsor monitors, Sponsor representatives, and partners, as well as the EC of each study site for review, as needed.

10. ORIGINAL DOCUMENTS, STUDY MONITORING AND QUALITY ASSURANCE

10.1. Source data record

Source data refers to all the information found in source files and certified copies of source files containing clinical findings, observations, or other activities that are part of the clinical study and which are necessary for study reconstruction and assessment. Source data is contained in source documents (comprising source documents and certified copies).

Source documents are original documents, data, and records (e.g., hospital records, medical histories and office records, laboratory notes, memoranda, patients' diaries or evaluation checklists, pharmacy dispensing records, recorded data from automated instruments, copies or transcriptions certified after verification as being accurate and complete, microfiches, photographic negatives, microfilm or magnetic media, x-rays, patients files, and records kept at

the pharmacy, at the laboratories, and at medico-technical departments involved in the clinical study).

The Sponsor's quality assurance group may assist in determining whether electronic records generated using computerized medical record systems used at investigational sites can be considered source documentation for the purposes of this protocol.

If the site computerized medical record system has not been adequately validated for the purposes of clinical research (instead of general clinical practice), all paper source documentation should be kept on file to ensure that important protocol data entered on the CRFs can be verified.

At a minimum, source documentation must be available to substantiate patient identification, eligibility, and participation; proper informed consent procedures; dates of visits; adherence to protocol procedures; adequate reporting and follow-up of AEs; administration of concomitant medication; study drug receipt/dispensing/return records; study drug administration information; and date of completion and reason.

Data recorded on the CRF will be verified by checking the CRF entries against source documents (i.e., all original documents, laboratory reports, medical records) in order to ensure data completeness and accuracy as required by study protocol. The investigator and/or site staff must make CRFs and source documents of patients enrolled in this study available for inspection by Sponsor or its representative at the time of each monitoring visit.

The source documents must also be available for inspection, verification, and copying, as required by regulations, officials of the regulatory Health Authorities [e.g., US Food and Drug Administration(FDA), EMA, and others], and/or ECs. The study investigator and site staff must comply with applicable privacy, data protection, and medical confidentiality laws for use and disclosure of information related to the study and enrolled patients.

The patient must also allow access to the patient's medical record. Each patient should be informed of this requirement prior to study start.

10.2. *Study monitoring and source data verification*

Sponsor or its representative will monitor study progress as frequently as necessary to ensure:

- Protection of study patients' rights and well-being.
- Study data are accurate, complete, and verifiable from the source documents.
- Conduct of the trial is in compliance with the approved protocol/amendment, good clinical practices (GCP), and applicable regulatory requirements.

Study staff contact details are included in a document located on the investigator site file

Data recorded on the CRF will be verified by checking the CRF entries against source documents (i.e., all original documents, laboratory reports, medical records, patients' diaries) in order to ensure data completeness and accuracy as required by study protocol. The investigator and/or

site staff must make CRFs and source documents of patients enrolled in this study available for inspection by the Sponsor or its representative at the time of each monitoring visit.

10.3. Record retention

Investigators should retain all study records in a secure place with restricted access as per applicable regulatory requirements. The investigator must consult a Sponsor representative before disposal of any study records and must notify the Sponsor (of any change in the location, disposition, or custody of the study files.

Essential documents must be retained by the investigator for at least two years after the last approval of a marketing application in an ICH region and until there are no pending or contemplated marketing applications in an ICH region, or at least two years have elapsed since the formal discontinuation of clinical development of the investigational product. "Essential documents" are defined as those documents which individually and collectively allow for the assessment of the conduct of the study and the quality of the resulting data. These documents must be retained for a longer period if required by the applicable regulatory requirements or as a result of an agreement with the Sponsor. It is the Sponsor's responsibility to notify the investigator or site when these documents are no longer needed (ICH E6 Guidelines, 4.9.5).

The study site investigator should not dispose of records belonging to this study without first (1) obtaining written approval from the Sponsor (2) offering the Sponsor an opportunity to collect these records. The study site investigator will be responsible for retaining suitable and accurate electronic or paper copies of source documentation containing observations and data collected from this study.

10.4. Data quality assurance

During the study or upon its completion, the quality assurance auditor(s) designated by Sponsor or the competent authorities may wish to perform an audit of the sites. Investigators are expected to cooperate in these audits, offering their assistance, and providing auditors with the documentation they require (including source documents).

The Sponsor's representatives are responsible for contacting and visiting the investigator in order to inspect the facilities and, upon request, to inspect clinical trial records (e.g., CRF and other pertinent data), provided that patient confidentiality is respected.

The investigator agrees to cooperate with the monitor to ensure that all issues detected during these monitoring visits are resolved, including delays in completing CRFs.

In accordance with the ICH E6 Guideline for GCP and the Sponsor's audit plans, the Sponsor's Department of Quality Assurance or its representatives may perform an audit of this study. An inspection of site facilities (e.g., pharmacy, drug storage areas, laboratories) and review of study-

related records will be carried out in order to assess the conduct of the study and compliance with the protocol, the ICH guidelines for GCP (ICH E6), and relevant regulatory requirements.

11. DATA MANAGEMENT

11.1. *Data entry and processing*

In this study, the investigator and/or site staff will regularly enter all data into the CRFs.

The investigator must review all data included in the CRF to ensure its accuracy.

Reconciliation of the data will be performed by the designated CRO. At the end of the study, any protocol non-compliances will be identified and recorded as part of the clinical database. Once all of these tasks are complete and the accuracy and completeness of the database has been verified, it will be locked and the data will become available for data statistical analysis.

11.2. *Data clarification*

As part of the conduct of the trial, Sponsor may have questions about the data entered by the site, referred to as queries. The monitors and the Sponsor are the only parties that can generate a query.

11.3. *Data coding procedures*

Coding of AEs, medical history, and prior and concomitant medications will be performed using standard dictionaries described in the data management plan.

12. STUDY MANAGEMENT

12.1. *Study discontinuation*

MedSIR reserves the right to discontinue the study at any time for safety or administrative reasons. If the study is discontinued and/or the site is closed for any reason, all of the investigational study drugs can be destroyed locally at the site according local law regarding radioactive products). All of the actions needed to assess or maintain study patient safety will continue as required, despite study discontinuation.

12.2. *Protocol amendments*

Any change or addition to the protocol requires a written protocol amendment or administrative letter that must be approved by Sponsor, the global scientific coordinator, the study site investigator, and the EC/Health Authorities when applicable. This requirement should not, under any circumstances, prevent any immediate action taken by the study site investigator or Sponsor to ensure the safety of all the patients enrolled in the study. If, in the opinion of the study site investigator, an immediate protocol amendment is required and it is applied for safety reasons,

this process should be reported to Sponsor as soon as possible (within 24hours) and the EC will be informed, as needed.

12.3. *Publication policy and protection of trade secrets*

All of the data generated by this study should be considered highly confidential and should not be disclosed to persons who are not directly related to the study without prior written permission from the global scientific coordinator and Sponsor. Nevertheless, full access is granted to authorized officials of Health Authorities, the global scientific coordinator or study site investigator, and Sponsor staff (or their representatives) for record inspection and copying. All of the investigational products, patient body fluids and/or other collected materials will only be used in accordance with this protocol, unless otherwise agreed in writing between the global scientific coordinator or study site investigator and Sponsor.

The Sponsor will ensure that, as far as possible, the study results are published in the form of scientific/clinical articles in prestigious scientific peer-reviewed journals. These documents will be prepared with the full participation of the principal investigators and in accordance with applicable guidelines for good publication practice and with international recommendations, such as those from the International Committee of Medical Journal Editors (ICMJE) and all elements of the Consort Statement (2010).

The Sponsor will be notified of any attempt to publish data obtained during the study and permission to do so must first be obtained from the Sponsor before publication.

12.4. *Insurance*

The Sponsor contracts an insurance policy to cover the responsibilities of the investigator and other parties participating in the study, according to the applicable Spanish legislation.

- Insurance company: CHUBB Insurance Company of Europe SE. [name].

Appendix 1: Schedule of study assessments and procedures

Study Period	Screening	Treatment period		Follow-up period		
Day	-28 to -1	Each cycle* (every 28 days)	End of treatment **	Every 3 months (Efficacy FUP) ¹²	At time of DP**	EoS (Safety FUP) ¹³
Informed Consent ¹	X					
Baseline signs/symptoms	X	X	X	X	X	
Check of inclusion/exclusion criteria	X					
Brief pain inventory (short form) (BPI-SF)	X					
Medical History ²	X					X
Physical Examination and ECOG status ^{3,4}	X	X	X	X	X	

Study Period	Screening	Treatment period		Follow-up period				
Day	-28 to -1	Each cycle* (every 28 days)	End of treatment **	Every 3 months (Efficacy FUP)¹²	At time of DP**	EoS (Safety FUP)¹³		
Concomitant Medication Reporting ⁵	X	X	X	X	X			
Health-related quality of life (HRQoL) questionnaire ⁶	X	X	X	X	X			
AE reporting ⁷	X	X	X	X	X	X		
Radiological Tumor Assessments ⁸	X	every 3 cycles	X	X	X			
Standard Laboratory Procedures								
Hematology ^{9,^}	X	X	X	X	X			
Biochemistry ^{10, ^}	X	X	X	X	X			
PSA determination [^]	X	X	X	X	X			

Study Period	Screening	Treatment period		Follow-up period			
Day	-28 to -1	Each cycle* (every 28 days)	End of treatment **	Every 3 months (Efficacy FUP) ¹²	At time of DP**	EoS (Safety FUP) ¹³	
Testosterone determination [^]	X						
Treatment Administration							
Radium-223 at dose of 55 kBq/Kg one IV injection		D1 (for a total of six IV injections)					
Research Central Laboratory Procedures							
Blood sample collection (split variant AR-V7 determination) ¹¹	X		X		X		
Blood sample collection (CTC count) ¹¹	X		X		X		

-
- * All visits must occur within \pm 7 working days from the scheduled date.
 - ** If disease progression coincides with the end of treatment visit, the evaluations planned for both visits will coincide, they will only be performed once (including blood sample for central laboratory).

 - ^ Local laboratory tests scheduled for day 1 of all cycles must be performed within 72 hours prior to confirm to the patient if treatment can be followed up.
 - 1. Signed written informed consent obtained prior to any trial-specific procedure.
 - 2. Complete medical history and demographics (including age, gender, and ethnic origin) and all medications taken the last 28 days prior to enrollment will be collected.
 - 3. Physical examination and vital signs (including respiratory rate, blood pressure measurements, heart rate, and body temperature) and weight measurement will be performed prior to enrollment.
 - 4. ECOG performance status will be assessed before trial drug administration and before the administration of each cycle.
 - 5. Relevant concomitant medication will be recorded at screening and on an ongoing basis.
 - 6. FACT-P, Version 04
 - 7. All AEs occurring during the trial and until the treatment discontinuation visit (end of study visit) have to be recorded with grading according to NCI-CTCAE version 4.0.
 - 8. Baseline assessments of the thorax, abdomen, and pelvis (preferably CT or MRI in case of contrast allergy) must be performed no more than 28 days before the first trial treatment. Baseline bone scan must be performed no more than 28 days before the first trial treatment. Post-baseline assessments have to be performed every 12 weeks \pm 7 working days after the first dose using the same imaging method and where possible obtained at the same institution for an individual patient as used during screening until progression disease. Radiographic bone progression will require the persistence of new lesions on a confirmatory scan at least six weeks later. In those patients who receive 6 treatment cycles, the radiological tumour assessment corresponding to week 24 will be performed for the EOT visit.
 - 9. Hematological test will be performed as per local standard of care and clinical indication before treatment administration. These values should be included: hemoglobin, hematocrit, red blood cell count, platelet count, and white blood cell count with differential count (neutrophils, lymphocytes, monocytes, eosinophils, and basophils).
 - 10. Biochemistry test will be performed as per local standard of care and clinical indication before first treatment administration and first day of follow-up. These values should be included: coagulation, chemistry with renal function analysis (serum creatinine, creatinine clearance according to the Cockcroft-Gault formula), liver function (AST, ALT, ALP, direct and total bilirubin), glucose, sodium, potassium, calcium, chloride, magnesium, uric acid, total protein, albumin, and lactate dehydrogenase.
 - 11. Blood sample for central laboratory prior to the start of study treatment, at the end of treatment and at time to documented progression disease (if the patient ends treatment due to progressive disease, only one blood sample will be sent at this point).
 - 12. After end of treatment (if no progressive disease documented), efficacy follow-up visits will be performed every 3 months including radiological tumour assessments until disease progression.
 - 13. After disease progression, a safety follow-up visit will be performed within three following months and 24 months after last dose of treatment to evaluate symptomatic skeletal related events, overall survival and post-study anticancer therapy.

Appendix 2: Response Evaluation Criteria in Solid Tumors Guidelines (RECIST criteria) (version 1.1)

Eisenhauer, E.A., et al., *New response evaluation criteria in solid tumours: revised RECIST guideline (version 1.1)*. Eur J Cancer, 2009. 45(2): p. 228-47.

Appendix 3: Instructions for blood sample collection. Detection of CTCs

CTC analysis will be conducted using high definition system to identify CTCs(HD-CTCs). It is distinct in that it does not rely on any single protein enrichment strategies. Instead, all nucleated cells are retained and immunofluorescently stained with monoclonal antibodies targeting cytokeratin (CK), an intermediate filament found exclusively in epithelial cells, a pan leukocyte specific antibody targeting CD45, and a nuclear stain, DAPI. All nucleated blood cells are imaged in multiple fluorescent channels to produce high quality and high resolution digital images that retain fine cytologic details of nuclear contour and cytoplasmic distribution. This enrichment-free strategy results in high sensitivity and high specificity, while adding high definition cytomorphology to enable detailed morphologic characterization of a CTC population known to be heterogeneous. A key advantage of this approach is that multiple analysis parameters can be pursued to identify and characterize specific populations of interest.

Blood samples (10 mL) will be collected using standard streck cell-free DNA BCT by venipuncture. The first 5 ml of blood collected from the fresh venipuncture cannot be used for the collection into de Streck tubes due to possibility of contaminating epithelial cells during venipuncture. These samples will be stored at room temperature and ship on day of collection in shipper at ambient temperature (date and time of draw are required) to Covance Central Laboratory Services (Switzerland) and they will be received and processed within 24 hours.

Blood sample processing for HD-CTC detection

Blood specimens will be rocked for five minutes before a WBC will be measured using the Hemocue white blood cell system (HemoCue, Sweden). Based upon the WBC count, a volume of blood will be subjected to erythrocyte lysis (ammonium chloride solution). After centrifugation, nucleated cells will be re-suspended in PBS and attached as a monolayer on custom made glass slides. The glass slides will be the same size as standard microscopy slides but have a proprietary coating that allows maximal retention of live cells.

Each slide can hold approximately three million nucleated cells, thus the number of cells plated per slide depend on the patients WBC. For HD-CTC detection, four slides will be used as a test. The remaining slides created for each patient will be stored at -80°C for future experiments.

Four slides will be thawed from each patient, then cells will be fixed with 2% paraformaldehyde, permeabilized with cold methanol, and non-specific binding sites will be blocked with goat serum. Slides will be subsequently incubated with monoclonal anti-pan CK antibody (Sigma) and CD45-Alexa 647 (Serotec) for 40 minutes at 37°C. After PBS washes, slides will be incubated with Alexa Fluor 555 goat anti-mouse antibody (Invitrogen) for 20 minutes at 37°C. Cells will be counterstained with DAPI for 10 minutes and mounted with an aqueous mounting media.

Detection of AR-V7 in CTCs

mRNA expression analyses will be performed using the ProstateCancerDetect kit with multiplexed reverse-transcription polymerase-chain-reaction (qRT-PCR) primers to detect the presence of CTCs, and custom primers designed to detect the full-length-AR (AR-FL) and AR AR-V7. The relative AR-V7 transcript abundance will be determined by calculating the ratio of AR-V7 to AR-FL.

Details will be provided in the study laboratory manual. All samples will be labelled with patient study number, date and time of collection.

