8.4. Efficacy results

Primary endpoint

We will analyze PFS in both cohorts with one arm Log-Rank test. This time endpoint will be described with Kaplan-Meier method. We will calculate number and proportion of events and median survival time, with corresponding 95% CI.

Secondary endpoints

We will describe the number and percentage of patients with AR-V7 mutation and CTCs at the start and at the end of the study. The evolution of these measures in the study will be analyzed with McNemar's test and paired odds ratio (OR) with corresponding 95% CI.

OS, time to first symptomatic SSE, rPFS and alkaline phosphatase level response (AF) will be described with Kaplan-Meier method. Number and proportion of events and median survival time, with corresponding 95% CI, will be calculated.

Subgroup analysis

The AR-V7-negative and positive cohorts at baseline will be compared for all analysis. For timed endpoints (PFS, OS, time to first symptomatic SSE, TTP-AF, and TTP-PSA), we will use the Kaplan-Meier method and Log-Rank test. For binary outcomes we will use chi-squared or Fisher's exact tests.

Levels of CTCs at the start and at the end of the study will be correlated with timed and binary endpoints. For timed and binary endpoints we will use Cox analysis and logistic regression, respectively.

We also analyse PFS and OS with multivariable Cox proportional hazards models for adjusting for AR-V7 status, CTCs levels and relevant baseline covariates, including Gleason score, PSA level, number of prior hormonal treatments, the presence or absence of visceral metastases, the Eastern Cooperative Oncology Group (ECOG) score, prior use of abiraterone acetate or enzalutamide, and the level of full-length (FL) androgen receptor. All tests were two-sided, and P values of 0.05 or less were considered to indicate statistical significance. We will examine the residuals to assess model assumptions and only first-order interactions will be evaluated. We will calculate relative risk (RR) and HR with corresponding 95% CI to compare dichotomous and time to event variables, respectively. Up-to-date versions of R will be used to conduct analyses.

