### Modified full analysis set

All patients with determination of CTC that accomplish selection criteria and receive at least one drug dose.

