#### **Molecular aspects:**

- Assessment of AR-V7 mutation prior to the start of study treatment and at time to documented progression disease or treatment end.
- Determination changes in CTCs number prior to the start of study treatment and at time to documented progression disease or treatment end.
- The molecular analysis will be conducted on the modified full analysis set.

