#### **Methods for secondary efficacy analysis and molecular aspects.**

The PFS, OS, time to first symptomatic SSE, rPFS and alkaline phosphatase level response (AF) will be described with Kaplan-Meier method. Number and proportion of events and median survival time, with corresponding 95% CI, will be calculated. We will describe the number and percentage of patients with AR-V7 mutation and CTCs at the start and at the end of the study. The evolution of these measures in the study will be analyzed with Mc Nemar's test. The 95% confidence interval for the difference of proportions will be based on the Wald with Bonett-Price Laplace adjustment. All tests were will be one-sided, and P values of 0.025 or less were considered to indicate statistical significance. If there are very few AR-V7 patients recruited, outcomes will be only described.

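### The AR-V7 evolution analysis has no category for samples without detectable CTCs, so loss or gain of CTCs can be reported as AR-V7 conversion

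*Protocol*

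**What the plan says.** Protocol Appendix 3, under the heading on detecting AR-V7 in CTCs, describes a multiplexed qRT-PCR assay. Its kit has "primers to detect the presence of CTCs, and custom primers designed to detect the full-length-AR (AR-FL) and AR AR-V7". The readout is a ratio: "The relative AR-V7 transcript abundance will be determined by calculating the ratio of AR-V7 to AR-FL". The appendix gives no positivity cut-off and no rule for a sample without CTC or AR-FL signal. It adds: "Details will be provided in the study laboratory manual".

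Protocol 8.4 sets out the summary: "We will describe the number and percentage of patients with AR-V7 mutation and CTCs at the start and at the end of the study". It continues: "The evolution of these measures in the study will be analyzed with McNemar's test and paired odds ratio (OR) with corresponding 95% CI". The SAP, under its methods for secondary efficacy and molecular aspects, keeps the test ("The evolution of these measures in the study will be analyzed with Mc Nemar's test"). It adds a confidence interval for the difference of proportions and uses one-sided testing at 0.025, whereas Protocol 8.3 makes tests two-sided by default.

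SAP 7.2.1 (Molecular aspects) assigns the population: "The molecular analysis will be conducted on the modified full analysis set". SAP section 6 defines that set as "All patients with determination of CTC that accomplish selection criteria and receive at least one drug dose".

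Two other rules bear on the point. Protocol 8.1 and 8.2 divide the expected 52 patients into 13 AR-V7-positive and 39 AR-V7-negative, with no third group. SAP 8.5 fills a status missing at baseline from the end-of-treatment or progression sample, and treats a status that is never available as negative. It does not cover a status missing only at the end.

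**The concern.** AR-V7 transcript can be found in this assay only if CTC material is present. With no AR-FL transcript the ratio has no denominator. A CTC-free sample is therefore uninformative about AR-V7, which is not the same as negative.

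McNemar's test needs a yes or no at each time. If a CTC-free sample is entered as no, a baseline-positive patient whose CTCs disappear counts as positive-to-negative. A patient without CTCs at baseline who later has AR-V7-positive CTCs counts as negative-to-positive. In both cases the discordant pair reflects CTC clearance or appearance, and change in CTC number is already a separate molecular endpoint.

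At stake is the meaning of the AR-V7 evolution endpoint. A treatment that only lowered CTC burden could be reported as reversing AR-V7, and a rising burden could be reported as AR-V7 emergence.

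**Working it through.** **1. The plan's own number.** The evolution test has no stated sample size or power. The relevant figure is the 13 expected positives in Protocol 8.2: 0.25 × 52 = 13. This can be reproduced from the primary-endpoint inputs (median 3 versus 6.3 months, one-sided alpha 0.05, power 80%, 23 months' accrual plus 11 months' follow-up) with an exponential log-hazard test. Events needed = (1.645 + 0.842)² / [ln(3/6.3)]² = 11.23. The probability of an event under the alternative is 0.892, so n = 11.23 / 0.892 = 12.6, rounded up to 13, and 13 / 0.25 = 52.

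**2. Are CTC-free samples in the analysis set?** The set requires a CTC determination, and a count of zero can be read as one. The same set and the same test serve both AR-V7 and CTCs. A McNemar test of CTC presence is informative only if some patients lack CTCs at one of the two times. So the set has to be able to hold CTC-free samples, and no rule removes them from the AR-V7 comparison.

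**3. What each possible coding does to the pair (start → end).**

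| Pattern | CTC-free coded negative | CTC-free treated as not available, SAP 8.5 applied | CTC-free not evaluable, no imputation |
|---|---|---|---|
| AR-V7-positive → no CTCs | positive → negative (discordant) | end status missing; no rule given | out of the test, shown in shift table |
| no CTCs → AR-V7-positive | negative → positive (discordant) | later status carried back: positive → positive | out of the test, shown in shift table |
| no CTCs → no CTCs | negative → negative | never available: negative → negative | out of the test, shown in shift table |

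The documents do not choose between the first two codings. Concordant pairs do not affect McNemar's test, but they enter the denominator of the difference in proportions and dilute it.

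**4. Illustration under the first coding.** Assume no true AR-V7 change, b clearances among positives and no opposite conversions. The exact McNemar p is then 0.5^b one-sided and 2 × 0.5^b two-sided.

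- b = 5: 0.031 one-sided, 0.0625 two-sided. Not significant at one-sided 0.025 or two-sided 0.05.
- b = 6: 0.0156 one-sided, 0.031 two-sided. Significant at both, provided the SAP's unstated one-sided direction is positive-to-negative.

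The continuity-corrected chi-square also needs six (two-sided p = 0.041; 0.074 at five). The uncorrected chi-square needs only four (0.0455). The SAP does not say which version will be used.

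If each of 13 positives has a paired sample and clears CTCs with probability q, the chance of at least k clearances is the sum from j = k to 13 of C(13, j) q^j (1 − q)^(13 − j):

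| Assumed q | Expected clearances (13q) | P(6 or more) | P(4 or more) |
|---|---|---|---|
| 10% | 1.3 | 0.1% | 3.4% |
| 20% | 2.6 | 3.0% | 25.3% |
| 30% | 3.9 | 16.5% | 57.9% |
| 40% | 5.2 | 42.6% | 83.1% |
| 50% | 6.5 | 70.9% | 95.4% |
| 60% | 7.8 | 90.2% | 99.2% |

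If CTC-free samples are not evaluable, the number of such false conversions is zero whatever q is.

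**The case against.** A reader might infer that the plan counts CTC clearance as conversion to AR-V7-negative. The documents do not say that. They are silent on the coding, and SAP 8.5 already recognises an unavailable AR-V7 status. If a CTC-free sample were placed there, an end-only gap would leave no pair, unless some unwritten rule filled it. The two written imputations give concordant pairs, so the SAP 8.5 default does not itself create a conversion. The laboratory manual, which is not among the documents, may define evaluability, and the kit's CTC primers could serve as that check. All of this stands, and it limits the point to what the plan permits.

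A reader might also infer that the trial could never separate clearance from true AR-V7 change. That goes too far. CTC count and AR-V7 are sampled at the same visits (Protocol Appendix 1), so the data allow a cross-tabulation. What is missing is an analysis that uses it.

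The size is also uncertain. No clearance rate is given, and the later samples are drawn at end of treatment and at progression, so high clearance cannot be presumed. Opposite conversions among the other 39 patients would offset the effect. The endpoint is secondary and outside the decision rule, and the SAP falls back to description if very few AR-V7 patients are recruited, though it gives no number for this. Described proportions would be confounded in the same way.

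Finally, restricting the test to pairs with CTCs at both times conditions on something treatment may change. That is a real limitation of the remedy.

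**Conclusion.** The point holds as a gap in the analysis, not as a stated miscoding. AR-V7 is read from CTC mRNA and the evolution comparison is binary. Its population must be able to include CTC-free samples, and nothing distinguishes absent CTCs from AR-V7-negative CTCs. The two-group split of all 52 patients, the default to negative when status is never available and the silence on end-only gaps allow a change in CTC burden to be reported as AR-V7 conversion.

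The possible size runs from negligible to dominant. Six one-way clearances among 13 positives suffice for significance with an exact test, and the chance of that runs from 0.1% to 90% over assumed clearance of 10% to 60%. These figures assume that CTC-free samples are coded negative, all 13 positives have paired samples, AR-V7 does not truly change and no conversions go the other way. They illustrate the mechanism and do not predict the result. The primary analysis and the trial's decision rule are unaffected. The change is worth making because it is cheap and settles what the endpoint means.

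**What to change.** In SAP 7.2.1:

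- Classify each sample as (a) no CTC or no AR-FL signal, not evaluable for AR-V7; (b) CTCs present, AR-V7-negative; or (c) CTCs present, AR-V7-positive. Refer to the laboratory manual for the calls.
- Report the 3x3 start-to-end shift table for all patients with paired samples.
- Run McNemar's test and the difference in proportions on pairs evaluable at both times, without the SAP 8.5 imputation of AR-V7 status.
- Show the all-patient binary version as a sensitivity analysis.

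The assay in Appendix 3 already targets CTC presence and AR-FL, so no new sampling is needed. The sponsor should confirm that both results reach the analysis database: Protocol 8.4 lists the full-length receptor level as a model covariate, but SAP 7.2.2 does not.

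The cost is fewer pairs, a wider interval and a test conditional on CTCs still being detectable after treatment. That conditioning should be stated when the result is interpreted, with the shift table showing who was left out.
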